Demographic and identifying information will be collected with a dedicated form (see Attachment 7 – participants details form). This information is collected in order to follow the guidelines of our funding agency, the National Institute of Mental Health (NIMH), with regard to data sharing and reporting. Identifying information, such as date and place of birth and full name in birth, is collected in order to get a GUID for data sharing in the NIMH Data Archive (NDA). GUID is a subject ID allowing researchers to share data specific to a study participant without exposing personally identifiable information and match participants across labs and research data repositories. This identifying information will not be publicly released.

To safeguard privacy, identifying information of participants will be stored in a password protected file on our secure servers and/or in locked filing cabinets in a locked room, to which only the Principal Investigator and members of the research team have access.

Study data will be stored in separate files from those with identifying information and will be collected and stored indefinitely on our secure servers. Participants' identifying information will not be directly connected to the data, and we will identify individual cases with alphanumeric codes. Video data will be stored in a password-protected area on our secure servers, with access only to the research team. Non-identifiable features will be extracted and coded for analysis, and then combined with other study data. De-identified data may be published and shared in public repositories for scientific purposes, as required by our funding agencies and scientific journals; however, no identifying information will be publicly released, so the risk that anyone would be able to identify specific participants is minimal.

c. Describe the plan for storage or destruction of data upon study completion:

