The behavioral research procedures as described in the research plan will be carried out in the laboratory utilizing the 2020 re-opening plans and COVID-19 protection protocols as long as these are in place. We will strictly follow Dartmouth College's policies. We hope to enroll 10 voluntary participants, from the college / surrounding community or from subpopulations, as allowed by COVID-19-related policies at the time of recruitment and participation.. Equipment utilized for these behavioral interventions include, as described above, Thermode systems, the BioPac Acquisition System, cameras (GoPros and a Thermal camera) and computers. Cleaning procedures for these devices are in place as part of the lab's approved reopening plan and will be strictly followed (see Attachment2- CANlab phase 2A lab reopening worksheet_9.2.2020]).

4. Analysis

Describe any qualitative tests and measures as well as quantitative methods:

Data will be analyzed via univariate and multivariate regression models as well as statistical learning-based classification techniques and Bayesian analyses. All data will be processed, analyzed and visualized using a combination of Excel, R, JAGS, Python, Matlab and similar software.

5. Study Progress Monitoring

Note: appropriate monitoring may include periodic assessment of the following:

- data quality
- timelines
- recruitment and enrollment

Provide a description of the methods which will be used to determine the progress of the study, including periodic assessments of data quality, timelines, recruitment, and enrollment as appropriate:

Study progress will be periodically monitored. We will test the timeline and protocol of the study before recruiting participants. Following the collection of data from the first participants and sessions, we will visually observe the data and run preliminary analyses to ensure data quality. Those steps will allow us to make informed decisions about potential study alterations. Since we plan to collect extensive data from each participant, and taking into account the challenges and restrictions of participants' recruiting during these unpredictable times, we may change the planned compensation or the number and duration of sessions and amend this protocol accordingly. Those aspects will be monitored continuously by the research team.

6. Risks & Benefits

Note: Risks may be physical, psychological, social, legal, economic, to reputation, or others.

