a. Describe any potential risks, their likelihood and seriousness:

Burn due to thermode malfunction: There is a very slight risk to the participant in case of thermode malfunction. Thousands of participants are tested using this equipment (Pathway, Q-Sense

and TSA2 systems, Medoc, Inc.) annually throughout the U.S. and the entire world, usually without adverse events. However, several reported cases of thermode malfunction have occurred in the past 5 years (four cases, to our knowledge), which have resulted in minor 1st or 2nd degree burns. The manufacturer (Medoc, Ltd.) has responded to these reports by building in enhanced hardware safety mechanisms; thus, we do not anticipate a substantial risk. The PI's lab has conducted experiments on more than 1,000 participants over the past 10 years with no adverse events. Although it is not possible to precisely determine the probability of a burn, we estimate based on our prior experience that it is considerably below 1%. We also note that the vast majority of potential burns that could potentially result from equipment malfunction would consist of minor blistering that would heal naturally without any treatment within several days. In addition, in the unlikely event that thermal heat becomes too intense for participants to tolerate, they will easily be able to stop the stimulus by releasing a strap to remove the thermode from their body. In conjunction with the software and hardware protocols built into the system by the manufacturer, we believe this procedure to be highly effective in ensuring minimal risk to participants.

Psychological discomfort: Studies involving administration of pain by definition require the induction of psychological discomfort, so this is an unavoidable risk of participation. However, as described above, the level of pain administered is calibrated to always be within participants' tolerable level, and participants are informed that they are free to discontinue the experiment at any time should they wish and can immediately stop any stimulus, if desired.

There are no known less risky alternatives to the use of any of the procedures proposed in these experiments that would provide comparable scientific information.

b. Confirm that risks to subjects have been minimized, by use of procedures which are consistent with sound research design and which do not unnecessarily expose subjects to risk:

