- causing distress in interviews of a sensitive nature

Describe potential events and provide a plan of action:

Although we do not anticipate adverse events, we will follow reporting standards. In any case of thermodes malfunction/burn, we will stop the study and assess potential for harm to future participants. As this is a known, however very rare risk, we do not consider it as an adverse event under formal definition. Nonetheless, we will inform IRB on any such event and will investigate the incident to make sure all safety procedures are strictly followed. If necessary, we will change the protocol of the study to prevent future such incidents.

An experimenter will always be present a few feet away from the testing room in which the experiment will take place. In addition, Dick's House (on campus health services) is across the parking lot from Moore hall. Participants will be sent there should they report any symptoms of physical or mental discomfort. Any psychological, social or medical services required will be available through Dick's House and/or referral to Dartmouth Hitchcock Medical Center.

8. Deception

Does any part of this study involve deception or withholding of information from participants?

 $\boxtimes \underline{Yes}$ \Box No

If Yes, provide an explanation which addresses the following:

- A description of the deception being used
- Why the deception is necessary
- A plan for debriefing, or providing subjects with the pertinent information after participation

In the some of the tasks, we will lead participants to be believe that a cue is predictive of lower or higher heat intensities, where in fact some of the cues will not be predictive of actual heat intensities. This minimal deception is critical to test the effect of different types of suggestions/conditioning on pain perception, because the management of participants' expectations and beliefs is a one of the main focuses of the study. Participants will be debriefed about this procedure and the intended purpose of the study upon the study's conclusion (see debrief form).

9. Equitable Participant Selection

- a. Estimated number of participants at Dartmouth CPHS reviewed sites:
 - 5-10

b. Provide a justification of the proposed sample size

As described above, this study is designed as a "N-of-few" experiment to study effects on pain perception over time. This design is also in line with the current guidelines and required precautions

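### Protocol Section 7 says a thermode burn is not an adverse event because it is known and rare, while Section 6a by implication counts burns as adverse events; one sentence should be replaced

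*Protocol*

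**What the plan says.** **Protocol Section 7 (Unexpected Events or Incidental Findings).** The answer opens by saying that adverse events are not anticipated and that reporting standards will be observed; it does not name the standards. It continues: "In any case of thermodes malfunction/burn, we will stop the study and assess potential for harm to future participants". The next sentence classifies the event: "As this is a known, however very rare risk, we do not consider it as an adverse event under formal definition". Then: "Nonetheless, we will inform IRB on any such event and will investigate the incident". The protocol will be changed if necessary.

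**Protocol Section 6a (Risks & Benefits, burn due to thermode malfunction).** Use of the equipment worldwide is described as "usually without adverse events. However, several reported cases of thermode malfunction have occurred in the past 5 years". The text puts these at four to the authors' knowledge and adds of them: "which have resulted in minor 1st or 2nd degree burns". The laboratory, it says, "has conducted experiments on more than 1,000 participants over the past 10 years with no adverse events". The following sentence puts the probability of a burn well under 1%, on the strength of prior experience.

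**Elsewhere.** Protocol Section 4 ("Data will be analyzed via univariate and multivariate regression models") and Section 5 ("run preliminary analyses to ensure data quality") do not mention harms. The SAP's two paragraphs concern pain ratings. Neither document defines an adverse event or says how a burn would be recorded or presented in the results.

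**The concern.** The two sections use one term in different ways. Section 7 removes a burn from the category because it is known and rare. Those properties make an event expected and infrequent; they do not settle whether a participant was harmed. On the protocol's own reasoning, a burn would be an expected adverse event rather than no adverse event.

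What is at stake is the safety statement in the results. A burn is the only physical injury that the protocol names as a risk, and the study applies painful heat in ten sessions per participant. If a burn occurred, a results report that took its definition from Section 7 could truthfully, by that definition, say that there were no adverse events. A reader would take that to mean that nobody was injured.

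**Working it through.** The point is textual; the arithmetic only sets its size.

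**1. The two sections side by side.**

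| | Section 7 | Section 6a |
|---|---|---|
| Is a burn an adverse event? | No, in a formal sense that is not reproduced | Yes, by implication |
| Basis | The risk is known and very rare | Burns are given as the exception to use without adverse events |

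The implication in 6a has two strands. First, the burns follow the word *However*, directly after the statement about use without adverse events. Second, the laboratory's record of no adverse events is the only experience of its own that it cites before estimating the burn probability. That record supports the estimate only if a burn would have counted as an adverse event.

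**2. Does the 6a figure hold together?** Inputs: 0 events and n = 1,000 (Section 6a says more than 1,000; a larger n lowers the limit). Exact one-sided 95% upper limit:

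1 − 0.05^(1/1000) = 0.00299, or 0.30% per participant.

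This agrees with an estimate well under 1%, provided that the zero includes burns.

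**3. How likely is a burn in this study?** Inputs: 5 to 10 participants (Section 9a) and the 0.30% limit. Assumptions: a participant here carries the same risk as a past participant, and participants are independent.

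- 5 participants: 1 − (1 − 0.00299)^5 = 1.5%
- 10 participants: 1 − (1 − 0.00299)^10 = 3.0%

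These are ceilings, because they use the upper limit. The documents do not say how many sessions past participants had. If the same limit applied to each session instead (50 to 100 sessions here), the ceilings would be 1 − (1 − 0.00299)^50 = 13.9% and 1 − (1 − 0.00299)^100 = 25.9%. The point does not depend on which is right.

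**4. What would one burn look like in the results?** With exact (Clopper-Pearson) two-sided 95% intervals:

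- 1 of 10 participants: 10% (0.25% to 44.5%)
- 1 of 5 participants: 20% (0.5% to 71.6%)

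Under Section 7 as worded, the adverse-event count in either case would be 0.

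**5. Does the general promise repair this?** The undertaking on reporting standards comes in the sentence about adverse events. Two sentences later burns are taken out of that category. The unnamed standards might require a burn to be reported whatever Section 7 calls it, or might apply only to what Section 7 calls an adverse event. The text does not settle which.

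**The case against.** The best case for the plan is that Section 7 answers a template question about unanticipated events. In that setting, *known* most naturally explains why a burn is not unanticipated, and the authors may simply have chosen the wrong term. The mention of a formal definition marks a technical sense, whereas 6a is ordinary risk description and never states outright that a burn is an adverse event. Section 7 deals with handling and IRB notice and sets no explicit rule for what a results report must say. The SAP describes the main analysis and does not bar reporting an injury.

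Much of this stands, and it keeps the point small. It does not save the sentence: if *unanticipated* was meant, the text still says something else, and the reason given does not support what it says.

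A reader might infer four stronger things, none of which the documents support:

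- *That a burn would go unnoticed or unreported.* Section 7 stops the study, informs the IRB of any such event and investigates.
- *That the burn estimate in 6a is wrong, or that past burns were left out of the record.* The wording of 6a points to zero burns, and the estimate agrees with that.
- *That Section 7 misapplies its formal definition.* The definition is not shown, so this cannot be checked.
- *That nothing else in the plan could bring a burn into the results.* The general promise on reporting standards might. The SAP's silence on safety covers every harm and is not caused by Section 7.

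**Conclusion.** The inconsistency is real and its severity is minor. Section 7's classification rests on a reason about expectedness, conflicts with the sense implied in 6a, and is not clearly overridden by the promise on reporting standards. Followed literally, it would permit a statement of no adverse events in a study where one participant in 5 to 10 had been burned. The conclusion rests on reading 6a by implication and on a results report adopting Section 7's sense of the term; neither is explicit. Participant protection is unaffected, as are the endpoints, analyses, sample size and stopping action. The effect is confined to how an unlikely event would be labelled and reported.

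**What to change.** In Section 7, replace the classifying sentence with: *A burn from the thermode is a known, expected adverse event; it will be recorded and reported as such, in addition to stopping the study and informing the IRB.* A malfunction that injures no one can stay outside the term, with the same stop and notice as now. If an institutional definition does exclude burns, cite it and use the term in the same way in 6a.

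Two additions are optional: a line in the SAP giving the number of participants with a burn or other skin injury, and a count of burns and malfunctions in 6a in place of the general statement about the laboratory's record.

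The cost is one sentence, with no new staff or participants; the optional 6a count would come from the laboratory's own records. The drawback is presentational: one minor burn would appear as a 10% to 20% adverse-event rate with a very wide interval, so the count and a short description should accompany any percentage.

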N-of-few Study of Pain Perception (NOF)

NCT04664400

Statistical Analysis Plan

8/3/22

Statistical analysis plan

Our main statistical analysis will be focused on participants' pain ratings following high vs. low cues for each of the conditions (symbolic learning, conditioning, and instructions only). For each condition, we will report the mean and standard deviation across participants test for significant differences in pain ratings following low vs. high cues with paired t tests, using statistical threshold of alpha = 0.05.

For the counterfactual task, we will compare ratings of the same pain stimulus when it is the better vs. the worst alternative, reporting the mean and SD across participants for this difference, and testing for significance with a paired t test.

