- 3) Study how expectations and pain perception unfold over time following conditioning without suggestion. We hypothesize that by substantially increasing the number of conditioning trials and sessions, as well as using more distinctive stimuli, we will induce stronger effects for all or most participants. We further hypothesize that such pure experience-based conditioning will strongly affect physiological responses, but heat evoked responses may decrease due to physiological preparatory or stress responses evoked by the cues.
- 4) Study how counterfactual monetary and pain-related outcomes affect pain responses. We hypothesize that heat stimuli will be more painful when the alternative option is better (e.g. lower heat or gaining money) compared to when the alternative option is worse (e.g. higher heat or losing money).

3. Study Design

Describe all study procedures, materials, and methods of data collection:

[figure not shown]
General design and procedures

This study is an "N-of-few" study, with a few participants completing 10 sessions each. The study includes four main components:

- 1) "Dose response".
- 2) Videos affective ratings task.
- 3) Cue-pain conditioning.
- 4) Counterfactual task.

The first part (~15 minutes) of each session will be dedicated to the "dose response" component. The second part of each session (~15 minutes) will be dedicated to the video watching task. The third part of each session (~30 minutes) will be dedicated to the cue-pain conditioning component. Finally, the last part of sessions 7-10 (~20 minutes) will be dedicated to the counterfactual task. The first session will also include a first part of consent, general instructions and demonstrations, to familiarize participants with the

experimental procedures and ensure that the heat stimuli we deliver to them during the experiment are tolerable. The four components will be described in detail below.

Across components 1, 3 and 4, participants will experience thermal pain stimuli delivered to different sites on their arms / legs. Pain stimuli will be delivered using a contact thermode (Medoc, Inc.; see details about the system below) that is placed against the skin. During and / or following stimuli, participants will be asked to rate how painful, intense and/or unpleasant was the stimulus they perceived. Prior to onset of some of the stimuli, participants will be asked to rate the expected intensity and their confidence in these expectations.

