For each participant, each cue will be paired with a distribution of low or a distribution of high heat stimuli in one of three ways: pure instructions, symbolic learning and/or experience-based conditioning. We will then test how each of these pairing methods affect anticipatory and pain responses across time following the different cues. We will also include an additional neutral cue that will not be paired with any intensity, to serve as a baseline condition. The "cue-pain conditioning" component will include the four following tasks:

[figure not shown]
 Symbolic learning: This task will be similar to previous studies in our lab ^{4,9}. Low/high cues will be paired with pictures of thermometers showing low/high temperatures, respectively, without pain delivery. These cues will not be predictive of actual intensity in the following tasks that will include heat stimuli.

- 2) *Conditioning*: Low/high cues will be paired with heat stimuli taken from low/high intensity distributions, respectively, without suggestion. These cues will be predictive of actual intensity in the conditioning task, but not in the test task (see below).
- 3) *Test*: All cues will be presented in this task in a pseudo-random order and will be proceeded by heat stimuli with moderate intensity. This will allow us to compare the effect of the different cues on expectations and pain responses evoked by the same moderate stimuli. More than one moderate temperature will be used in the test task, to ensure that heat intensity affects pain responses, and pain reports are not driven by demand characteristic.
- 4) *Cues recognition*: In this task, all cues will be randomly presented one by one and participants will be asked to rate how hot they expect the stimulus paired with this cue to be. This task will be used to test explicit learning, in addition to the expectation ratings during the test task.

In the pure instructions condition, participants will be instructed for each cue whether it is paired with low or with high heat stimuli, without further conditioning. These cues will not be predictive of actual intensity in the following tasks.

In order to control for order effects between the symbolic learning and conditioning tasks, their order will be counter-balanced across sessions and participants (see below).

The structure of the tasks across the 10 sessions will be as follow (the order of the symbolic learning and conditioning tasks will change between participants):

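### Does the SAP's high-versus-low cue comparison let the truly hotter conditioning-task stimuli into the conditioning contrast?

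*SAP*

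**What the plan says.** The SAP's cue analysis is two sentences long. Its focus is "pain ratings following high vs. low cues for each of the conditions (symbolic learning, conditioning, and instructions only", and it tests each condition's "pain ratings following low vs. high cues with paired t tests, using statistical threshold of alpha = 0.05". No task, session or temperature is named.

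The rest of the design is in Protocol section 3, under Cue-pain conditioning:

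- **Conditioning task:** "Low/high cues will be paired with heat stimuli taken from low/high intensity distributions, respectively, without suggestion". The protocol adds: "These cues will be predictive of actual intensity in the conditioning task, but not in the test task".
- **Symbolic learning task:** cues are paired with thermometer pictures, and no heat is delivered.
- **Instruction cues:** participants are told what each cue means, and no conditioning follows.
- **Test task:** all cues appear in pseudo-random order with moderate heat. The protocol says this task is what makes it possible to compare the cues' effects on responses to identical moderate stimuli. It also says: "More than one moderate temperature will be used in the test task".
- **Schedule:** conditioning runs in sessions 1-6 and the test task in sessions 1-10.

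On ratings, General design and procedures says of components 1, 3 and 4 together that "participants will be asked to rate how painful, intense and/or unpleasant was the stimulus they perceived". Component 3 is the cue-pain component.

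**The concern.** Taken on its own, the SAP's rule covers any pain rating that follows a high or low cue. Conditioning-task trials fit that description if they are rated, and the general statement about ratings makes this likely. On those trials the high cue really does bring hotter heat, so the high-minus-low difference would be positive with no expectancy effect at all.

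Only the conditioning condition is exposed, since the other two cue types never precede heat that differs by cue. The three main results would then measure different things. The error would also run towards the protocol's third hypothesis, that many conditioning trials with distinctive stimuli produce stronger effects, and more distinctive stimuli would enlarge it.

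A second, smaller worry is that the test task pools several moderate temperatures with no temperature term in the analysis.

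**Working it through.** **1. Where can each cue type produce a pain rating?**

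| Cue type | Learning stage | Test task |
|---|---|---|
| Symbolic | No heat, so no pain rating | Moderate heat |
| Instruction | Instruction only, so no pain rating | Moderate heat |
| Conditioning | Low or high heat according to cue; rating likely but not stated for this task | Moderate heat |

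The cue recognition task asks only for expectations. The test task is therefore the only source of pain ratings common to the three conditions that the SAP puts under one rule. It is also the task that the protocol designates for comparing cues.

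**2. What would pooling do?** The documents state no power or rejection figure to reproduce, so every input here except the session counts, the sample sizes and alpha is an assumption. Let w be the share of conditioning-cue ratings that come from the conditioning task, D the temperature-driven high-low rating difference on an assumed 0-100 scale, and S the SD of participants' differences. With no true cue effect:

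- bias = w × D
- standardised difference = w × D / S
- rejection probability from the noncentral t with n − 1 degrees of freedom, alpha 0.05 (two-sided assumed).

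The protocol gives n as 5-10 (section 9a), with 10 hoped for (section 3).

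With equal rated trials per task per session, w = 6/(6 + 10) = 0.375. If the conditioning task has half as many trials as the test task, w = 3/13 = 0.231; if twice as many, w = 12/22 = 0.545. At w = 0.375, D = 10, 20 or 40 gives a bias of 3.75, 7.5 or 15 points.

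The rejection rate depends heavily on S. For w = 0.375 and D = 20 (bias 7.5):

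- With a between-person SD of 8 for D and a residual SD of 3, S = √((0.375 × 8)² + 3²) = √18 = 4.24. The standardised difference is 7.5/4.24 = 1.77, and the test rejects with probability about 0.83 at n = 5 and above 0.99 at n = 10.
- With S = 10, it is 7.5/10 = 0.75, and the probabilities are 0.25 and 0.56.

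Other settings:

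| w | D | S | Bias | n = 5 | n = 10 |
|---|---|---|---|---|---|
| 0.25 | 10 | 10 | 2.5 | 0.07 | 0.11 |
| 0.25 | 20 | 10 | 5 | 0.14 | 0.29 |
| 0.50 | 20 | 10 | 10 | 0.40 | 0.80 |
| 0.50 | 30 | 5 | 15 | >0.99 | >0.99 |
| 0 (test task only) | any | any | 0 | 0.05 | 0.05 |

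**3. Do several moderate temperatures bias the test-task contrast?** If ratings rise by b points per degree, a participant's high-minus-low difference is the cue effect plus b × (mean temperature after high cues − mean temperature after low cues). The second term is zero when temperatures are balanced across cues. The protocol says that conditioning cues do not predict intensity in the test task and that symbolic and instruction cues never do, so temperature is not tied to cue. Any chance imbalance would add noise, with no systematic direction.

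**The case for a change.** The best case for a change is that an SAP should fix its own trial set. This one shows that its authors knew how: the next paragraph, on the counterfactual task, holds the pain stimulus constant, and the cue paragraph does not. Protocol section 4 lists only broad families of methods and settles nothing. The possible error favours a study hypothesis, and one sentence would close the gap.

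Much of this stands. The SAP is silent on the task, pooling would be a real confounding, and its direction is as described.

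What does not stand is the step from silence to inclusion. The SAP nowhere says that all ratings are used or that conditioning-task trials enter. To pool them, an analyst would have to pass over the protocol's stated purpose for the test task and apply one rule to different kinds of trial in different conditions. Nor does the SAP plan a test between conditions, so any ranking of conditioning above the other two methods would be informal.

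**Conclusion.** No change to the plan is needed. The SAP leaves out a detail that the protocol supplies: the cue comparison belongs to the test task, where the heat is moderate after every cue. On that reading the temperature bias is zero and the test keeps its 0.05 level with respect to this issue. A sentence in the SAP would record that analysis without altering it.

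The range of 0.07 to above 0.99 for false rejection (w = 0.25-0.5, D = 10-30, S = 5-10) applies only if conditioning-task ratings were pooled. It also rests on assumed trial shares, rating differences and SDs, so no single value in it should be cited as the plan's error rate.

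The conclusion rests on two points: that the SAP is read together with its protocol, and that moderate temperatures in the test task do not depend on the cue. The protocol supports both. Evidence that conditioning-task ratings had entered the main contrast would reverse it.
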